The split-mouth design compares treatments within each patient, avoiding bias that may arise when comparing separate cases and controls. It eliminates inter-subject variability and produces reliable results (Kazancioglu et al., 2014; Lesaffre et al., 2007). Compared to between-patient designs, the split-mouth design offers increased efficiency, requiring fewer participants and resources while achieving similar results. However, it also presents the potential for carry-across effects, where the treatment on one side of the mouth influences the response on the other side (Hujoel & Loesche, 1990; Varma & Chilton, 1974). To estimate treatment effects in a split-mouth design, researchers make assumptions about carry-over effects. Common assumptions include no carry-over effect, complete carry-over effect, and partial carry-over effect. These assumptions cannot be tested within the study itself and rely on prior knowledge (Hujoel & DeRouen, 1992).

When choosing a split-mouth design, researchers should consider bias, recruitment challenges, efficiency, and statistical analysis. Careful evaluation of potential carry-over effects is crucial to avoid bias. Finding suitable patients with symmetrical dental conditions can be difficult, and statistical analysis requires more complex methods compared to whole-mouth designs (Hujoel, 1998). Controlling carry-over effects in split-mouth studies is challenging. Washout periods of at least three weeks between treatment applications can help mitigate carry-over effects by allowing the body to eliminate residual effects of previous treatments (Gozali et al., 2017). Understanding the advantages, limitations, statistical considerations, and implications of the split-mouth design is essential for researchers in both the statistical and clinical fields. This knowledge

enables effective utilization of the design while acknowledging its potential drawbacks (Lesaffre et al., 2009).

Chapter 3:

Material and Methods

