3.1. Study Design

This clinical trial will utilize a split-mouth design, randomly assigning two different treatments to each half of the patient's mouth. From this randomized study which is characterized by a triple-blind study, the procedures are going to be performed by qualified and experienced professional. However, the operator will have no access to data evaluated. The evaluator will have access to all responses of the symptoms of patients and will not know the treatment that is going to be selected, while the patient is unaware of which treatment or intervention is being applied to each side of their mouth. This stringent blinding approach minimizes potential biases and significantly enhances the scientific validity of the study.

Patients will be assigned into two groups and each patient acted as their own control using the split-mouth technique. One impacted third molar will be removed from one side and will receive conventional drugs while the other side will be removed after 3 weeks (wash-out period) and receive additional treatment beside the conventional drugs (i.e., either enzyme or herbal). The two groups will be classified as follows:

- The first group will receive conventional drugs with 10mg oral serratiopeptidase at immediate post-operative time and three times a day for post-operative five days on the first surgical visit and on the second surgical visit (after 3 weeks) conventional drugs will be given only or vice versa.
- The second group will receive conventional drugs with 20mg oral escin at immediate post-operative time and three times a day for post-operative five days on the first surgical visit and on the second surgical visit (after 3 weeks) conventional drugs will be given only or vice versa.

The conventional drugs, it will be administered to patients in the two groups, includes: Amoxicillin 500mg Cap b.i.d., Metronidazole 500mg Tab t.i.d., Diclofenac sodium 50mg Tab b.i.d.

3.2.Study Population

The study population will include patients who will visit the dental clinics in the College of Dentistry, University of Science and Technology, Yemen (USTY) for impacted mandibular third molars extraction during 2024.

3.3.Sample Size

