The sample size is the number of participants planned to be included in the trial, usually determined using a statistical power calculation (Zanatta et al., 2017). This study determined the sample size using a power calculation based on previous research by (Costa et al., 2015). Their study found that preemptive use of etoricoxib 120mg significantly reduced the need for rescue analgesic medication compared to a placebo (1.6 ± 1.3 vs 4.0 ± 2.5). To achieve a power of 80% and a confidence interval of 95%. The study will need to evaluate 11 surgical sites per sub-group (<http://www.openepi.com/SampleSize/SSMean.htm>). To account for a potential 20% drop-out rate, a total of 14 sites per sub-group will be recruited. This will result in a total sample size of 56 dental units (2 teeth per patient) from 28 patients. The following Table 3-1 illustrates the study sample size and the planned treatment.

Table 3-1 : Sample Size and Study Treatment.

Groups	I		II		Total
Patients	14		14		28
Sub-groups	Control 1	Study 1	Control 2	Study 2	4
Sample size	14	14	14	14	56
Conventional Treatment	Amoxicillin 500mg Cap b.i.d		Metronidazole 500mg Tab t.i.d		N/A
	Diclofenac sodium 50mg Tab b.i.d				
Study Treatment	N/A	Serratiopeptidase 10mg t.id	N/A	Escin 20mg t.id	N/A

3.4.Sample Selection

Patients who will undergo to surgical removal of the impacted third molar will be assessed for their eligibility to participate according to the following inclusion and exclusion criteria:

Inclusion criteria:

- Medically fit patients.
- The presence of two asymptomatic mandibular third molar indicated for surgical extraction.
- Absence of pericoronitis or signs of inflammation during the last 30 days

Exclusion criteria:

- Patient administered other drugs such as NSAIDS and steroids.
- Patient has allergy to the drugs used in this study.
- Pregnant patient or a patient with lactation.
- Immunocompromised patients with diabetic or hypertension (from patient's history).
- Patients with irradiated maxillofacial region.
- Intellectually disabled patients and patients unable to come for follow up visits.
- Patients with acute and subacute pericoronitis

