3.5. Randomization

This clinical trial will utilize simple randomization based on the technique described by (Oliveira et al., 2021). This method involves drawing envelopes to determine the following:

- Surgical site: Test or control side
- Tooth: Right third molar ("A") or left third molar ("B")
- Surgery order: First or second session

The following steps of randomization will be followed:

1. Draw the tooth: An envelope is drawn to determine which third molar will be extracted first (right or left).
2. Draw the intervention: A second envelope is drawn to determine whether the selected tooth will receive the test intervention ("X-1") or no intervention ("X-2").
3. Draw the surgery order: A final envelope is drawn to determine whether the selected tooth will be extracted in the first or second surgery session.

3.6.Pre-operative and Post-operative Assessment

Prior to surgical removal of impacted third molar, preoperative variables (i.e., pain, trismus, and facial swelling) will be taken for each patient and recorded in the data collection sheet. Furthermore, the same post-operative variables (preoperative variables) will be taken immediately after the procedure, 2nd day, 3rd day and 5th day after the operation. Both pre-operative and post-operative variables will be done by the same measurements.

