3.7. Surgical Procedures

To minimize variability and bias, all surgical extractions will be performed by the same oral surgeon utilizing a uniform technique (Isola et al., 2019). Each patient will receive similar operative procedures under identical conditions, including administration of local anesthetic consisting of inferior alveolar, lingual, and long buccal nerve blocks. Additionally, the same surgical procedure will be adopted for all groups. Access to the third molar will be achieved from the buccal aspect. A mucoperiosteal flap will be raised, and bone removal with a round bur in a straight handpiece under continuous irrigation with a sterile saline solution and/or tooth sectioning will be performed. After tooth extraction, the alveolus will be inspected, curetted for granulation tissue removal, and irrigated with a sterile saline solution. The surgical wound will be closed using a 4–0 reabsorbable suture (Coated VICRYL). This meticulous approach minimizes intraoperative trauma and ensures consistency across all groups.

Post-operatively, patients will receive their assigned medications and receive thorough instructions regarding dietary restrictions (liquid and cold diet for 24 hours), oral hygiene practices, and avoidance of mouthwashes to prevent bleeding. They will be informed about potential complications and instructed to contact the surgeon if any issues arise. Additionally, they will be requested to report any physical symptoms experienced during the study period.

3.8.Ethical Consideration

The ethical approval will be obtained from the USTY Medical Research Ethics Committee. The purpose and methodology of the study will be explained to all the participants. Hence, a participant information sheet (Appendix B) will be given to all participants and a written informed consent form (Appendix C) will be obtained from them with the tenets of the revised Declaration of Helsinki 1975.

3.9.Statistical Method

Quantitative data (pain, trismus, and facial swelling) will be expressed as means and standard deviations and compared using the paired t test (parametric) or Wilcoxon test (nonparametric). The Shapiro–Wilk test will be used to verify the normality of the data. A difference of $P < .05$ will be considered statistically significant. The data analysis will be performed using SPSS V.25 (SPSS, JASP).

References

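### The planned paired tests leave out session (first or second surgery): valid on average over the random order, but the estimate is shifted by a session effect when the order drawn is uneven, and power is lost if that effect is not small

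*Combined protocol and SAP*

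**What the plan says.** Section 3.1 has each patient operated on twice, three weeks apart. Oral study drug is added after one surgery and not after the other: the added drug comes first and "on the second surgical visit (after 3 weeks) conventional drugs will be given only or vice versa". Section 3.5 calls the scheme simple randomization by envelope, and one item drawn is "Surgery order: First or second session". No blocking or other balancing of the order is described. Section 3.3 gives 14 patients, hence 14 pairs, in each of the two groups.

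Section 3.9 says that pain, trismus and swelling will be "compared using the paired t test (parametric") or with a Wilcoxon test as the nonparametric alternative, after a Shapiro–Wilk check, at P < .05. It mentions no session term, stratification by order or sensitivity analysis.

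Section 2.3 discusses carry-over and wash-out and remarks that for split-mouth trials "statistical analysis requires more complex methods compared to whole-mouth designs". It does not discuss a difference between sessions. The case sheet in Appendix A records the first and second visits separately.

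**The concern.** Because the drugs are taken by mouth and the sides are operated on at different times, each group is a two-session crossover. A paired test on drug minus control treats any general difference between first and second surgery as part of the data to be explained by drug. If the order is split evenly, the session effect cancels from the mean but stays in the variance, so the test loses power. If the split is uneven, part of the session effect stays in the estimate.

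A session effect is plausible, most clearly for pain, where a patient knows what to expect the second time. Groups of 14 with an unblocked order will often be uneven. The two groups can also be shifted by different amounts, which matters for the serratiopeptidase-versus-escin hypothesis in 1.5.

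**Working it through.** **The plan's own figure.** Section 3.3 takes "1.6 ± 1.3 vs 4.0 ± 2.5" from an earlier trial, with 80% power and 95% confidence. The independent-samples formula gives n = (1.96 + 0.84)² × (1.3² + 2.5²) / 2.4² = 7.85 × 7.94 / 5.76 = 10.8, so 11. Allowing for 20% drop-out, 11 / 0.8 = 13.75, so 14. The figure reproduces and is not disputed here. It contains no session term.

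**Model.** For each patient let d = drug minus control = τ + πs + e. Here s = +1 if the drug falls in session 2 and −1 if in session 1, π is the session 2 minus session 1 effect, and SD(e) = 1. All effects are therefore in SDs of the within-patient difference. Assumptions: π from 0 to 0.75, true effect τ = 0.8, two-sided 5%, normal data, no carry-over, and each order equally likely and independent between patients (the plain meaning of simple randomization).

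**Shift given the split.** The mean of d estimates τ + π(n₂ − n₁)/n, where n₂ and n₁ are the numbers with drug second and drug first. The chances are binomial with n = 14.

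| Split | Shift in the estimate | Chance of this split or worse |
|---|---|---|
| 7:7 | 0 | (exactly 7:7: 20.9%) |
| 9:5 | 4/14 = 0.29π | 42.4% |
| 10:4 | 6/14 = 0.43π | 18.0% |
| 11:3 | 8/14 = 0.57π | 5.7% |

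The chance that at least one of the two groups is 10:4 or worse is 1 − (1 − 0.180)² = 33%.

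**Noise.** Under random order the variance of d is 1 + π², which is 6% larger at π = 0.25, 25% at 0.5 and 56% at 0.75.

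**Adjusted estimate.** Average the two order-specific means of d. The shift is then zero at any split. The variance is (1/n₁ + 1/n₂)/4. At 7:7 this is 1/14 = 0.071, the same as for the paired mean. At 10:4 it is (0.100 + 0.250)/4 = 0.0875. One degree of freedom is spent (12 instead of 13). This is where the cost of adjusting comes from.

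**Power by simulation, unadjusted / adjusted (%).**

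| π | 14 pairs, simple order | 14 pairs, 7:7 | 11 pairs, simple order |
|---|---|---|---|
| 0 | 79.0 / 75.0 | 79.0 / 78.4 | 66.7 / 61.2 |
| 0.25 | 76.4 / 75.0 | 77.1 / 78.4 | 64.2 / 61.5 |
| 0.5 | 69.6 / 75.1 | 70.9 / 78.5 | 57.2 / 61.4 |
| 0.75 | 59.8 / 75.1 | 60.7 / 78.4 | 47.6 / 61.3 |

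Under simple order the two analyses break even near π = 0.32 with 14 pairs and between 0.35 and 0.4 with 11.

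**Type I error of the paired t test, given the split (14 pairs).** At π = 0.5 it is about 3% at 7:7, 5% at 9:5, 8% at 10:4 and 13% at 11:3. At π = 0.25 it is about 4%, 5%, 6% and 7%. Averaged over all splits it is 5% in both cases. The adjusted test is at about 5% throughout.

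**The case against.** The strongest reply is that randomizing the order already protects the paired t test. That is correct: over the randomization it is unbiased and holds 5%. A reader might infer from the missing session term that the planned test is invalid or biased in general, and the documents do not support that. The shift exists only given an uneven split. Even at π = 0.5, splits up to 9:5 (82% of draws) show no meaningful inflation of type I error, although at 8:6 and 9:5 the estimate is still shifted. What remains is that the one trial run will be read at its own split.

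A second reply is that the adjustment may cost more than it gains. This also stands in part. With order left unbalanced and a session effect below about 0.32 SD, the adjusted test has less power, and nothing in the documents says the effect is larger than that.

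A third reply is that the three-week interval and the pre-operative readings at each visit remove much of any residue from the first surgery. For trismus, defined in 3.6.2 as a before–after difference, that is at least partly so. It does not cover expectation in pain scores, and the wash-out is aimed at carry-over, which a session term does not address either.

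Finally, one sentence in 3.1 can be read as conventional drugs always first and the study drug always second. A reader might infer that session and drug are fully confounded. The same section allows the reverse order and 3.5 draws it, so this is an inconsistency to resolve and not an established fixed order.

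**Conclusion.** The concern holds in a limited form. The paired t and Wilcoxon tests in 3.9 are not wrong on average, but they ignore a feature of the design that is drawn at random and already recorded. In a group with a 10:4 split the estimate carries 0.43 of any session effect. With a balanced order and a session effect of 0.5 SD, the unadjusted test gives up about 8 points of power (71% against 78%) and is conservative, with a type I error near 3%.

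The mechanism is certain; the size is not. It rests on an assumed session effect and a true effect of 0.8 SD. If there is no session effect, nothing is lost by the plan as written. This is a worthwhile and cheap improvement, best made together with a balanced order, and not a flaw that invalidates the trial.

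**What to change.** 1. **Reconcile the order first.** In 3.1, the sentence that reads as conventional drugs first and study drug three weeks later must be reconciled with the statement that either order may occur and with 3.5. In 3.5, steps 1 and 3 both settle which session the selected tooth belongs to and must also be reconciled. Under a fixed order no analysis can separate session from drug.
2. **In 3.9, prespecify session (first/second) as a fixed term.** Either compare the session 1 minus session 2 differences between the two orders (half the difference in means is the drug effect), or fit a mixed model with treatment and session as fixed effects and patient as random effect. As the nonparametric fallback, use a rank-sum test of those session differences between the two orders in place of the Wilcoxon paired test. State that this is the main analysis, so that the choice is not made after the split is known.
3. **In 3.5, balance the order within each group,** for example with blocked envelopes, keeping the block size concealed.

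Cost: a change of wording in 3.9 and a different preparation of the envelopes. No new data, visits or patients are needed. If there is no session effect and the order stays unbalanced, adjustment loses about 4 points of power with 14 pairs and 5 to 6 with 11. With a 7:7 order the loss at 14 pairs is under 1 point.

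### The paired test in section 3.9 cannot compare serratiopeptidase with escin, the trial's general objective, and it drops patients who have only one session

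*Combined protocol and SAP*

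**What the plan says.** Section 3.9 (Statistical Method) states that the three outcomes will be "compared using the paired t test (parametric) or Wilcoxon test (nonparametric" as the alternative, with Shapiro-Wilk to choose between them. It adds: "A difference of $P < .05$ will be considered statistically significant". It names no time point, summary over days, session effect, rule for patients with one session, or between-group test.

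The rest of the plan sets what that analysis must handle:

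- **Questions.** Section 1.5 lists three hypotheses: each drug against conventional drugs alone, and serratiopeptidase against escin. Section 1.4 makes the comparison of the two drugs the general objective.
- **Design.** Section 3.1 puts patients in two groups. Within a group, one session has the group's drug plus conventional drugs and the other, three weeks apart, has conventional drugs alone. No patient receives both drugs.
- **Times.** Section 3.6 takes readings before surgery, immediately after, and on the "2nd day, 3rd day and 5th day after the operation".
- **Numbers.** Section 3.3: "The study will need to evaluate 11 surgical sites per sub-group", then "To account for a potential 20% drop-out rate, a total of 14 sites per sub-group will be recruited". That is 14 patients per group and 28 in all.
- **Allocation.** Section 3.5 draws the tooth, the intervention and the surgery order. It describes no draw to drug group.

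**The concern.** A paired test works on one difference per patient. That suits hypotheses 1 and 2, where each patient supplies a treated and a control session. It does not suit hypothesis 3, where the two drugs are in different people. With 14 patients in each group, software would accept two columns and return a paired result, but the pairing would depend on row order.

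The likely substitute is to set the two within-group p-values side by side and call the drug with the smaller one superior. That is not a test of the difference between drugs.

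A second, smaller matter is that the sessions are three weeks apart. A patient can complete the first and not return, and a paired test cannot use that patient's data.

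Third, the natural reading of 3.9 with Table 3-1 is a separate test for each group and each day. Section 3.9 does not say so; it is an inference from the four sub-groups and the absence of any summary measure.

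**Working it through.** **1. The plan's own figure.** Inputs from section 3.3: "compared to a placebo (1.6 ± 1.3 vs 4.0 ± 2.5", 80% power, 95% confidence (two-sided assumed).

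n = (1.3² + 2.5²)(1.960 + 0.842)² / (4.0 − 1.6)² = 7.94 × 7.85 / 5.76 = 10.82, rounded up to 11. Then 11 / 0.8 = 13.75, rounded up to 14. Both figures reproduce. The formula is for two independent means and the variable is rescue-analgesic use, so the plan contains no size or power for the drug-versus-drug contrast.

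**2. Comparing p-values is no substitute.** Suppose both drugs work equally well and each group's test has the planned 80% power. The groups are independent, so exactly one test is significant with probability 2 × 0.8 × 0.2 = 0.32. About one trial in three would then suggest a winner between equal drugs.

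**3. What a valid contrast looks like.** It is the difference between the two groups' mean within-patient differences. As an illustration, take the SDs in 3.3 and an assumed within-patient correlation of 0.5 (not in the documents):

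- SD of a within-patient difference = √(7.94 − 2 × 0.5 × 1.3 × 2.5) = 2.166
- one drug against control, 11 pairs: SE = 2.166/√11 = 0.653; half-width 2.228 × 0.653 = 1.45 (10 df)
- drug against drug, 11 pairs per group: SE = 2.166 × √(2/11) = 0.923; half-width 2.086 × 0.923 = 1.93 (20 df)

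The contrast can be estimated, but less precisely than either drug against control.

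**4. What one model adds to drug against control.** The model has one value per session, a random patient effect and variance pooled over both groups.

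- *All 14 pairs complete.* The SE ratio to the paired test is 1.000. Degrees of freedom go from 13 to 26 and the critical value from 2.160 to 2.056, a ratio of 0.951. By simulation the interval ratio is 0.959. So the interval is about 4-5% narrower. For an illustrative effect of 0.8 SD, power goes from 79% to 82%.
- *11 pairs plus 3 patients with session 1 only, per group.* SE ratios are 0.956, 0.968 and 0.981 at within-patient correlation 0.3, 0.5 and 0.7. Degrees of freedom go from 10 to 20 and the critical value from 2.228 to 2.086, a ratio of 0.936. The products are 0.895, 0.906 and 0.918. Simulated interval ratios run from 0.90 to 0.93 with coverage of 94-96%. So the interval is about 7-10% narrower. At correlation 0.5 the half-width of 1.45 becomes 1.32. Where the paired test has 80% power, the model has 85-87%.

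**5. A model that must be avoided.** Two sessions of three days give six readings per patient. With a patient intercept as the only random effect, readings within a session are treated as no more alike than readings from different sessions. Simulated with no true effect, the false-positive rate for the effect averaged over days was about 14%, 22% and 28% at between-day correlation 0.3, 0.5 and 0.7. A paired or two-sample t test on session means stayed near 5%.

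**The case against.** The strongest reply is that none of this requires a mixed model. With complete pairs, a two-sample t or Mann-Whitney test on within-patient differences answers hypothesis 3 and keeps the plan's simplicity. That is correct, and the fix allows it. But 3.9 names no such test. Its Wilcoxon test is given as the nonparametric partner of the paired t test, so the natural reading is the signed-rank test.

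Three stronger readings are tempting, and the documents do not support them:

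- **That the paired test wastes half the information.** It uses half the pooled degrees of freedom, but with complete pairs the SE is the same.
- **That a mixed model lifts power from 80% to 93%.** That gain comes from averaging three days at an assumed between-day correlation of 0.5, where the variance ratio is (3 + 6 × 0.5)/9 = 0.67, with an effect constant over days. A paired test on session means obtains it too.
- **That analysing completers biases the result.** Nothing in the plan says that patients with the worst first recovery leave. Section 3.5 draws the surgery order, so selection on the first session pulls in opposite directions in the two orders. In a simulation with balanced order and the worst 3 of 14 leaving, bias was about 0.02 SD with no effect and 0.05 SD on an effect of 0.8 SD. Section 3.3 has also budgeted for the loss: 14 are recruited so that 11 remain.

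**Conclusion.** The concern holds on its main point, which needs no assumption: followed as written, 3.9 has no test for hypothesis 3 or the general objective. It should be corrected before the data are analysed.

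The loss of one-session patients is real but minor. Keeping them lowers the SE by 2-4%, or narrows the interval by about 7-10% together with pooled degrees of freedom. This assumes that the 3 lost patients per group each have session 1, a within-patient correlation of 0.3-0.7, similar residual variance in the two groups, and missingness that depends only on observed data.

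A reader might infer that the plan has chosen separate tests by group and day. It has not stated that; the text is silent, and silence is what needs correcting. A reader might also assume that serratiopeptidase against escin is a randomised comparison. Section 3.5 does not support that, because none of its draws assigns the drug group.

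**What to change.** In section 3.9, for each outcome:

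1. Reduce each session to one pre-specified summary, for example the mean of days 2, 3 and 5, adjusted for that session's pre-operative value.
2. Fit one linear mixed model to all sessions of all patients: group, treatment within group and session order as fixed effects, patient as random effect, with Satterthwaite or Kenward-Roger degrees of freedom.
3. Estimate each drug against its own group's control, and drug against drug as the difference between the two within-patient effects. Do not merge the two control arms. With complete pairs, a two-sample t or Mann-Whitney test on within-patient differences serves for drug against drug.
4. If days are modelled separately, add a session-within-patient random effect or an unstructured covariance over days.
5. Keep the paired t or Wilcoxon test on complete pairs as a sensitivity analysis.
6. State in 3.5 how patients are allocated to drug group. Describe drug against drug as randomised only if that allocation is randomised.

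The cost is wording. The case sheet in Appendix A already records group, sub-group, visit, pre-operative value and every day, and SPSS, named in 3.9, can fit the model. The price is two assumptions to state in the SAP: similar residual variance in both groups, and missingness that depends only on observed data. Averaging over days also answers a question about the whole early recovery, so daily values should still be shown descriptively.

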1.5. Study Hypotheses

Based on the study main problem, objectives, and literature review, three main hypotheses are constructed in order to test the relationship between the study variables.

These hypotheses are listed in this section as follows:

1. There is a statistically significant difference in serratiopeptidase, when used in addition to conventional drugs, in reducing post-operative pain, trismus, and facial swelling compared to conventional drugs alone following impacted third molar surgery.
2. There is a statistically significant difference in escin, when used in addition to conventional drugs, in reducing post-operative pain, trismus, and facial swelling compared to conventional drugs alone following impacted third molar surgery.
3. There is a statistically significant difference in serratiopeptidase in reducing post-operative pain, trismus, and facial swelling compared to escin, when

both used in addition to conventional drugs, following impacted third molar surgery.

Chapter 2:

Literature Review

2.1.Impacted Third Molar

The third molars, commonly known as wisdom teeth, often lead to complications during eruption, presenting a frequent concern in oral surgery (Wray et al., 2003). (Lytle, 1979) defines an impacted tooth as “*a tooth that has failed to erupt into its normal functional position beyond the time usually expected for such appearance. Eruption may have been prevented by adjacent hard or soft tissue including tooth, bone, or dense soft tissue*”. Among impacted teeth, mandibular third molars are the most common, followed by maxillary third molars and maxillary canines. Most unerupted teeth are extracted due to pain or infection, but other reasons include involvement in pathologies like cysts or tumors, causing resorption of adjacent teeth, or interfering with surgical procedures (Undrell Moore, 2011).

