3.6.3. Assessment of Facial Swelling (Edema)

This outcome will be evaluated through using the method described by (Schultze-Mosgau et al., 1995) to quantify facial swelling pre- and post-operatively. Measurements will be taken with a flexible scale in the closed mouth position by marking five fixed points and three surgical base lines connecting the said fixed points as follows:

- 5 fixed points (F1 – tragus of ear, F2 – angle of mandible, F3 – soft tissue pogonion, F4 – Corner of mouth, F5 – lateral canthus of eye)
- 3 surgical base lines (S1 – from tragus of ear to corner of mouth, S2 – from tragus of ear to soft tissue pogonion, S3 – from lateral canthus of eye to angle of mandible).

[figure not shown]

Figure 3-3 Swelling Measurement.

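### Section 3.9 applies one unadjusted P<.05 rule with no primary outcome, time point or success rule; an ineffective drug's chance of a false benefit runs from about 0.1% to 26%, depending on a reading the plan never states

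*Combined protocol and SAP*

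**What the plan says.** Section 3.9 (Statistical Method) is the whole inferential plan. It says: "Quantitative data (pain, trismus, and facial swelling) will be expressed as means and standard deviations and compared using the paired t test", with the Wilcoxon test as the nonparametric alternative. It then sets the threshold: "A difference of $P < .05$ will be considered statistically significant". It mentions no time points.

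Section 3.6 says that the same three variables "will be taken immediately after the procedure, 2nd day, 3rd day and 5th day after the operation". Section 3.6.3 records swelling by "marking five fixed points and three surgical base lines connecting the said fixed points" and gives no rule for combining the three lines.

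Section 1.5 words each hypothesis over all three outcomes together. Hypothesis 1 reads "There is a statistically significant difference in serratiopeptidase, when used in addition to conventional drugs, in reducing post-operative pain, trismus, and facial swelling", against conventional drugs alone. Hypothesis 2 says the same for escin. Hypothesis 3 compares the two drugs: "There is a statistically significant difference in serratiopeptidase in reducing post-operative pain, trismus, and facial swelling compared to escin".

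Section 3.3 bases the sample size on a published trial in which the study drug "significantly reduced the need for rescue analgesic medication compared to a placebo". Rescue analgesic use is not among the outcomes in Section 3.6 and has no field in the case sheet (Appendix A).

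**The concern.** A threshold of P<.05 limits the error of one test. It limits the error of a claim only if the plan says which test, or which combination of tests, supports that claim. Here three outcomes are measured at four post-operative times for each of two drugs, and nothing says whether a hypothesis in Section 1.5 is met by one significant outcome on one day, by an average over days, or only by all three outcomes. The sample size cannot serve as an implied choice of primary outcome, because it uses a variable the trial does not assess.

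With 11 to 14 patients per drug, chance differences on single days are to be expected. If the reading is settled after the data are seen, a reader cannot tell what error rate stands behind a reported benefit. This matters more because Section 1.1 says the study is meant to give definitive answers.

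**Working it through.** **The plan's own figure.** Inputs from Section 3.3: means 1.6 and 4.0 (difference 2.4), SDs 1.3 and 2.5, 80% power, 95% confidence. For two independent means:

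n = (1.3² + 2.5²)(1.96 + 0.842)² / 2.4² = 7.94 × 7.85 / 5.76 = 10.8, so 11 per sub-group. Then 11 / 0.8 = 13.75, so 14.

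Both figures reproduce. They concern a single test of rescue analgesic use.

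**Counts.** Three outcomes (3.9) × four post-operative times (3.6) = 12 tests per drug; × two drugs (3.1) = 24. The plan states no count; this one comes from joining 3.9 to the visit schedule in 3.6.

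**Assumptions.** Neither drug works. Tests are two-sided at 5%, so 2.5% falls in the drug's favour (3.9 does not state sidedness). The documents give no correlations, so those below are assumed for the within-patient differences.

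**Uncorrelated measures, drug-favouring errors.**
- One drug, any of 12 tests: 1 − 0.975¹² = 26.2%.
- Both drugs, any of 24 tests: 1 − 0.975²⁴ = 45.5%.
- One drug, days averaged, any of 3 tests: 1 − 0.975³ = 7.3%.
- One drug, all three outcomes, each on at least one day: (1 − 0.975⁴)³ = 0.09%.
- One drug without the immediate time point, any of 9 tests: 1 − 0.975⁹ = 20.4%. Section 3.1 gives "10mg oral serratiopeptidase at immediate post-operative time and three times a day for post-operative five days", so the immediate assessment coincides with the first dose and can show little drug effect.

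**Correlated measures.** Simulated null trials with 14 patients per drug (11 gives nearly the same), normal differences, an exchangeable outcome-by-time correlation, and a one-sample t test of the differences. Figures are for one drug:

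| Assumed correlation, outcomes / times | Any of 12 tests | Days averaged, any of 3 | All three outcomes, each on at least one day |
|---|---|---|---|
| 0 / 0 | 26% | 7% | 0.1% |
| 0.3 / 0.5 | 20% to 21% | 7% | 0.3% |
| 0.5 / 0.7 | 16% | 6% | 0.6% |
| 0.8 / 0.9 | 9% to 10% | 5% | 1.4% to 1.5% |
| 0.9 / 0.9 | 8% | 4% | 2.2% |

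The two groups contain different patients, so the chance over both drugs is 1 − (1 − p)². At p = 0.21 this is 38%; at p = 0.08 it is 15%.

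**The case against.** The best reply is that Section 3.9 does not prescribe testing each day, and that Section 1.5 names the three outcomes jointly. On a joint reading the false-benefit rate is at or below the nominal 2.5%; on a day-averaged reading the excess is modest. The correlated figures also depend on correlations that no document supplies.

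All of this stands, and it limits the claim. A reader might infer that the plan literally calls for 24 tests, or that 26% is the trial's error rate. The documents support neither. The count of 24 is inferred. The 26% belongs to the 12 tests of one drug, with uncorrelated measures and any single result counting as benefit; over 24 tests the matching figure is 46%. A reader might also raise the count by testing the three swelling lines separately (20 tests per drug, 1 − 0.975²⁰ = 39.7%) or by testing Hypothesis 3 at each time, but Section 3.9 describes neither.

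The reply does not remove the problem. No section adopts the joint or the averaged reading, and the only rule given calls any difference with P<.05 significant. High correlation does not rescue the any-result reading either: at 0.9 throughout, the rate is still about three times 2.5%.

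**Conclusion.** The concern holds as a gap in the decision rule. The same P<.05 criterion implies a chance of a false benefit for one ineffective drug of:

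- 26% uncorrelated, or about 8% to 21% correlated, if any outcome at any time suffices;
- about 5% to 7% if days are averaged (4% at the highest correlation tried);
- about 0.1% to 2% if all three outcomes must favour the drug, each on at least one day.

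The reference is 2.5% for one two-sided test. The figures rest on the inferred test count, assumed two-sided testing and assumed correlations. The absence of a primary outcome, time point, success rule and multiplicity rule rests on the documents alone.

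**What to change.** **In Section 3.9, before any data are seen:**
1. Name one primary outcome, of the sponsor's choice, with one summary per surgery: for example the mean change from the pre-operative value over days 2, 3 and 5, or the change at one named day. If swelling is chosen, combine the three lines into one measure.
2. Test it once per hypothesis: a paired test of each drug against control, and for Hypothesis 3 a between-group comparison of the within-patient differences.
3. State whether 5% is held per hypothesis or across the three (for example by Holm).
4. Report all other outcomes and times as secondary, with estimates and 95% confidence intervals.

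**In Section 3.3:** restate power for that outcome and test, including Hypothesis 3, at the number expected after drop-out.

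**Cost.** A few sentences, no new data items, and fewer claims of significance. Held per hypothesis, the drug-favouring error is 2.5% per drug at the present level, and simulation puts the chance of any false difference among the three tests at about 12%. Held across the three, that chance is about 4%, but power falls.

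The only inputs available for pricing this are the protocol's rescue-analgesic figures. The SD of the difference is √(1.3² + 2.5² − 2r × 1.3 × 2.5) = 2.82 / 2.45 / 2.17 at assumed within-patient correlations r = 0 / 0.3 / 0.5. Power from the noncentral t distribution, for a difference of 2.4:

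| Test | Level | 11 per group | 14 per group |
|---|---|---|---|
| Drug vs control, paired | 0.05 | 72% / 83% / 91% | 84% / 92% / 97% |
| Drug vs control, paired | 0.0167 | 51% / 65% / 77% | 67% / 81% / 90% |
| Hypothesis 3, between groups | 0.05 | 48% / 59% / 70% | 58% / 71% / 81% |
| Hypothesis 3, between groups | 0.0167 | 30% / 40% / 51% | 40% / 52% / 65% |

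The level 0.0167 is Bonferroni, or Holm's first step; Holm's later steps are less strict. Hypothesis 3 is the weakest comparison even at 0.05. Figures for the chosen outcome may differ and should be stated. No increase in enrolment is proposed.
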